## **Data collection**

Patient characteristics. The following information will be recorded:

- Record number
- Age
- Checked inclusion and exclusion criteria
- Checked informed consent
- Histology: tumour type (ovarian or endometrial), differentiation grade, numbers of lymph node removed including sentinel node(s) including histological results specified per sentinel node
- FIGO stage

- Surgical findings: tumour side, injections side, result frozen section, time between injection and detection, sentinel node positive or not, number of sentinel nodes, first sentinel node blue, first sentinel node gamma detection, amount of gamma counts, complications during surgery, side effects during surgery.
- Postoperative scintigram, residual nodes, location of residual nodes.
- Result pathology nodes removed: benign or malignant.

The surgeon has to register the number and location of both sentinel nodes resected. For this purpose the surgeon has to draw the location of the lymph nodes in an anatomical drawing (see Figure 1 - page 20). Ten different locations will be used to report where the sentinel nodes were found:

1. high para-aortic
2. low para-aortic
3. interaortic-caval
4. para-caval
5. iliaca communis left
6. iliaca communis right
7. external iliaca left
8. external iliaca right
9. obturator left
10. obturator right

The surgeon also has to register the location of the lymphatic tissue removed, related to the lymph node sampling following the removal of the sentinel node(s).

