### Objective:

- 1) To determine whether or not a sentinel node procedure in patients with ovarian cancer is feasible when the tracers are injected in the ovarian ligaments.
- 2) To determine the anatomical localisations of the sentinel nodes.
- 3) To determine the incidence of false negative sentinel nodes.

**Study design:** phase I feasibility study.

**Study population:** the following patients will be included:

- Patients with a high suspicion of an ovarian malignancy in whom a median laparotomy and a frozen section analysis is planned.
- Patients with endometrial cancer in whom a staging laparotomy is planned.

**Intervention (if applicable):** After opening the abdomen, before starting the surgical staging procedure, blue dye and the radioactive-colloid will be injected in the ligamentum ovarium proprium and the ligamentum infundibulo-pelvicum. This will be done on the ovary with suspicion of malignancy (patients with an ovarian tumour) or one of the normal ovaries (patients with endometrial cancer).

**Main study parameters:** percentage of patients in whom it is feasible to identify sentinel nodes. Other study parameters are the anatomical localisation of the sentinel node(s) and the incidence of false negative lymph nodes.

**Nature and extent of the burden and risks associated with participation, benefit and group relatedness:** the surgery is prolonged with 20-25 minutes due to the required

incubation time after injection of the blue dye and radioactive isotope. A scintigram will be performed 24 hours after the surgery to determine whether residual radioactive lymph nodes

can be detected. The scintigram will only be performed if the patient is capable to be transported to the nuclear department. No extra blood samples will be taken, no extra visits, physical examinations or other tests are necessary. There is no risk of tumour dissemination by injecting the tracers in the ovarian ligaments. There is a 0,07 to 2,7% risk of an allergic reaction to the blue dye. The dose of radioactive isotope given does not give adverse side effects, either to the patients or the personnel present in the operating theatre.

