#### *During surgery*

Removal of lymph nodes:

- systematic lymphadenectomy / lymph node sampling

Approaches range from taking some lymph nodes only (lymph node sampling) to systematic lymphadenectomy [22]. A systematic lymphadenectomy can be seen as the golden standard. However, such a radical procedure gives more late morbidity than lymph node sampling. These include the formation of lymphocyst (up to 13.5%), nerve and vessel injury (up to 4%) and increased blood loss and operating time [26, 27].

- removal of sentinel node(s)

Through a sentinel node procedure the first node that receives primary lymphatic flow can be identified (the so called sentinel node). The pathological examination is an indication of the nodal status of the remaining nodes. If the sentinel node is negative, the patient may be spared a radical lymphadenectomy and thus the morbidity that can be caused by it [28].

The sentinel node technique has been proven effective in other cancers such as breast cancer and malignant melanoma. In the gynaecological field it has been shown to be effective in vulvar cancer. Currently sentinel node studies are done for cervix en uterine cancer. Studies done for sentinel node in ovarian cancer are very limited. One article that describes the role of sentinel lymph node sampling in gynaecological cancers, only briefly mentions ovarian cancer. The authors state that the procedure is difficult due to the often bulky mass ovarian tumours. Furthermore, with injecting in the ovary there is a possible risk of tumour dissemination [28].

*Nyberg et al.* have done a study in 16 patients with high-risk uterine cancer in which technetium and blue dye were injected in the right or left ovary [29]. They used an incubation time of 15 minutes. In this study patients were included with a high-risk uterine carcinoma because these patients obtain the same operation as patients with clinical early stage ovarian cancer: a total abdominal hysterectomy (TAH) with bilateral salpingo-oophorectomy (BSO) and a pelvic and para-aortic lymphadenectomy or lymph node sampling. In 15 out of 16 patients the sentinel node was detected. Another study used activated charcoal solution to identify ovarian lymphatics in 11 patients. The charcoal was injected in the cortex of the ovary. The charcoal was deposited in the lymph nodes of all patients [12].

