- Removal of the adnex and admittance to the pathologist for a frozen section analysis. (standard care)
- If the result is benign, no further actions will be performed in these patients and the procedure ends at this time. (standard care)
- If the result is malignant, the sentinel nodes will be identified either by the radioactive tracer and / or visually (blue dye). (extra for the study)
- The sentinel nodes will be removed. (standard or extra for the study, depending on whether or not the lymph node(s) would have been removed as part of the standard lymph node sampling)
- Subsequently a complete staging procedure will be performed. (standard care)

*Patients with endometrial cancer in whom a staging laparotomy is planned*

After making the median incision and opening the abdomen, blue dye and the radioactive isotope will be injected in the ligamentum ovarii proprium (median side) and the ligamentum infundibulo-pelvicum (lateral side) of one of the ovaries, in the same manner as described above in patients with a high suspicion of an ovarian malignancy. The choice of the ovary (left or right side) will switch between left and right by each patient who is included in the study.

A 15-minute interval will be planned after injection. In this time period at 5 and 10 minutes the radioactivity will be measured along the lymphatic tract to document whether or not perhaps sentinel node(s) can be identified at a shorter time-interval in future studies. The radioactivity is measured by a Geiger counter. The Geiger counter will be the same device in all surgeries.

After the 15 minutes time-interval the sentinel node(s) will be identified either (once more) by the radioactive tracer and / or visually (blue dye) after opening the retroperitoneal space.

After removal of the sentinel node(s) a complete standard staging procedure will be performed including a comprehensive at random sampling of other lymph nodes at the different locations.

Surgical steps related to the study (standard or extra):

- Median laparotomy (standard care)
- Injection of blue dye and radioactive isotope (extra for the study)
- 15 minute waiting time during the surgery (extra for the study)
- The sentinel nodes will be identified either by the radioactive tracer and / or visually (blue dye) (extra for the study)

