***Benefits and risks assessment, group relatedness***

The risk of the study are low, a small chance of 0.07-2.7% of an allergic reaction to the blue dye. The surgery will be prolonged with 20-25 minutes, which is without extra risk for the patient.

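### Removing extra sentinel nodes is a study procedure, but the risk statements omit it and the data list has no place for a complication that begins after surgery

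*Protocol*

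**What the plan says.** Under Surgical procedures, for the ovarian and the endometrial group alike, removing the sentinel nodes is labelled "standard or extra for the study, depending on whether or not the lymph node(s) would have been removed" in the standard sampling. The complete staging operation, with its own node sampling, then follows.

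Benefits and risks assessment states: "The risk of the study are low, a small chance of 0.07-2.7% of an allergic reaction to the blue dye". It continues: "The surgery will be prolonged with 20-25 minutes, which is without extra risk for the patient". The Summary gives the same allergy range, puts the extra minutes down to incubation time, denies any risk of tumour spread or isotope side effects, and adds: "No extra blood samples will be taken, no extra visits, physical examinations or other tests are necessary". Neither place mentions the removal of additional nodes. Adverse and serious adverse events also discusses only tumour spread and dye reactions.

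The Data collection list includes "complications during surgery, side effects during surgery". Its postoperative items are the scintigram and the pathology result. Handling and storage of data describes the study file as holding patient characteristics and surgical findings, and refers back to the data collection list.

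Safety reporting is wider. All serious adverse events go to the ethics committee within 15 days of first knowledge, with faster reporting for fatal or life-threatening ones. All adverse events are to be followed until they abate or stabilise. The annual progress report covers serious events and other problems.

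**The concern.** If a study procedure adds tissue removal to an operation, the risk assessment should say so, and the dataset should have somewhere to put the complications that might follow. Complications of node surgery need not show themselves in the operating theatre; a lymphocyst is the obvious example. As written, the ethics committee weighs a risk paragraph that leaves out one of the study's own procedures, and the investigators follow a data list whose complication window closes at the end of surgery.

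Two things are at stake. The first is the safety description in the final report: an absence of recorded postoperative complications could be read as an absence of complications, when no item asked for them. The second is consistency within the protocol: a rule to follow all adverse events has little to work on if non-serious events with later onset are never listed. The point has extra weight because the Introduction justifies the sentinel node concept by the morbidity that it may one day spare.

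**Working it through.** The protocol gives no design figure on this point, so the check is a comparison of texts.

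1. **Is extra node removal a study procedure?** Yes, in part. The step lists for both groups allow for a sentinel node that standard sampling would not have taken. How many such nodes there will be is not stated.

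2. **Do the risk statements cover it?** No. In the Summary and in Benefits and risks assessment, the burdens named are dye allergy (0.07 to 2.7%), 20 to 25 more minutes of surgery and, in the Summary, a scintigram. The claim that the longer operation adds no risk is absolute and comes with no support.

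3. **Which complications does the data list capture?**
   - Recognised during the operation (for example vessel injury or bleeding): yes, under the intra-operative item.
   - Serious, beginning after the operation: no item on the list, but reportable under Adverse and serious adverse events once known, and included in the annual report.
   - Non-serious, beginning after the operation: no item, no time window and no study visit intended to detect it. The last study contact described is the scintigram one day after surgery, done only if the patient can be moved.

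4. **Does the follow-up rule fill the third row?** Not by itself. It says how long a known event is followed. It does not say over what period events are sought or where they are recorded, and the study file is described by reference to the list that lacks the item.

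5. **What could the study say if the item existed?** With 20 evaluable patients and no events of a given kind, the one-sided 95% upper bound is 1 − 0.05^(1/20) = 0.139, or 13.9%. There is no comparator, so an observed complication could not be separated from the effect of the standard staging operation. Recording is therefore worthwhile for description and not for inference.

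**The case against.** The strongest reply is that safety is governed by the Safety reporting section and not by the data list. That section is not limited to the operation: it requires serious events to be reported from first knowledge and all adverse events to be followed, with extra tests or referral if needed. This stands for serious events. It does not supply an item or a window for non-serious ones.

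Several stronger readings are tempting, and the documents do not support them.

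- A reader might infer that the protocol itself names the late morbidity of the study procedure, and might multiply those rates by 20 patients. The Introduction does list "the formation of lymphocyst (up to 13.5%), nerve and vessel injury (up to 4%) and increased blood loss and operating time", but for systematic lymphadenectomy, of which it says that "such a radical procedure gives more late morbidity than lymph node sampling". This study prescribes sampling plus sentinel nodes. Upper figures for a different and larger operation do not measure the increment from a few extra nodes.
- A reader might infer that the study cannot see its own surgical harm. Intra-operative injury is recorded and known serious events are reported, so that goes too far.
- A reader might infer that the feasibility conclusion is compromised. The main parameter is the percentage of patients in whom sentinel nodes are identified, and no secondary objective concerns morbidity. Every evaluable patient still has full staging, so the study could not show that morbidity was spared, whatever it recorded.
- A reader might see a contradiction over operating time. The Summary attributes the added minutes to incubation, while the Introduction speaks of radical dissection. The claim of no added risk is unsupported, but the Introduction does not directly contradict it.

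**Conclusion.** The point holds in a limited form. Removal of nodes beyond the standard sample is partly a study procedure, and the risk statements are silent on it. The data list confines complications to the operation, which does not fit the rule that all adverse events are followed. The events left without a home are non-serious complications with onset after surgery.

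No numerical size can be given: the documents state neither the expected number of extra nodes nor a complication rate for removing them. That such removal may carry some added surgical risk is a reasonable assumption; the protocol gives no figure for it. The detection endpoint and its analysis are untouched. This is a modest defect in the safety description and the risk assessment, worth correcting mainly because the correction is cheap.

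**What to change.** Reconcile Data collection, Follow-up of adverse events, and Benefits and risks assessment.

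- In Data collection, extend the complication and side-effect item to run from injection through the routine postoperative check, with date of onset, taken from the hospital record. The protocol does not describe that check, so the sponsor should name the one already used in routine care. Apply the same window to adverse event collection.
- Report these complications descriptively and state that, without a comparator, they cannot be separated from the effects of standard staging.
- In the Summary and in Benefits and risks assessment, state that additional nodes may be removed and that this may carry added surgical risk. Delete the clause saying that the prolonged operation is without extra risk.
- Optionally, record for each sentinel node whether it was standard or extra. The sampling is at random, so this asks the surgeon what would otherwise have been removed; the tag is a judgement and should be presented as one.

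The cost is a few more items completed from routine records and a less favourable risk paragraph. No visit, test, patient or change to the surgery is added, so the Summary's statement that there are no extra visits remains true.

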### ***Staging***

In case of a clinical early stage ovarian cancer, the Dutch guideline [1] recommends a staging laparotomy with adequate lymph node sampling, with an absolute minimum of ten lymph nodes removed. In the same guideline, a footnote is made stating that a larger number of removed lymph nodes will increase the chance of finding metastases. These lymph nodes also need to be sampled from different anatomical regions, of which the most important are the

para-aortic and paracaval region between the renal vein and inferior mesenteric artery, the common, internal and external iliac vessels and the obturator fossa.

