***Secondary Objective(s)***

- The anatomical location(s) and number of the sentinel node(s):
  - visualized at surgery regarding blue dye
  - recorded by the gammaprobe at surgery radiocolloid
  - visualized at scintigraphy 24 hours after surgery regarding possibly remaining lymph nodes
- Incidence of false negative lymph nodes.

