### **3. STUDY DESIGN**

Observational feasibility study to detect sentinel nodes: mapping the lymphatic drainage of the ovaries.

The study will end after 20 patients, of which at least 10 patients with ovarian cancer, are included in which the complete sentinel node procedure has been performed. The expected inclusion period is estimated to be two years. If the detection rate of the sentinel node is less than 50%, or when less 5 patients are included in a year, the study will end prematurely.

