**5. METHODS*****Main study parameter***

To determine whether or not a sentinel node procedure in patients with ovarian cancer is feasible by injecting the tracers into the ovarian ligaments instead of into the ovary itself.

The lymphatic drainage of the ovary follows the lymph vessels that accompany the ovarian artery and vein in the infundibulopelvic ligament up to the high para-aortic region and renal vein. The exact mechanism of drainage to pelvic area is still unclear. It may follow the lymph vessels adjacent to the uterus towards the pelvic lymph nodes.

Through a sentinel node procedure the first node(s) that receives primary lymphatic flow should be identified (the so-called sentinel node(s)). In case of lymphatic spread, this lymph node will be the first lymph node obtaining a metastasis.

In this feasibility study we will include both patients with (suspicion of) ovarian cancer as well as patients with a high-risk uterine carcinoma. The latter group of patients can also be included because these patients obtain the same surgical procedure; a total abdominal hysterectomy (TAH) with bilateral salpingo-oophorectomy (BSO) and a pelvic and para-aortic lymphadenectomy of lymph node sampling.

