## **7. STATISTICAL ANALYSIS**

***Descriptive statistics***

Registered items:

- Sentinel nodes
  - o Number per patient
  - o Location(s) per patient
  - o Number(s) of sentinel nodes containing a metastasis per patient
  - o Location of sentinel nodes containing a metastasis per patient
- Non-sentinel lymph nodes removed during the subsequent staging procedure
  - o Number per patient
  - o Location(s) per patient
  - o Number(s) containing a metastasis per patient
  - o Location of non sentinel nodes containing a metastasis per patient

Based on the above registered items the median and mean number of sentinel nodes and its main locations can be determined. By combining the data of the sentinel en non-sentinel nodes, cases in which de sentinel node is false negative can be identified

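### The ten fixed locations for reporting sentinel nodes include no internal iliac region and no residual category

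*Protocol*

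**What the plan says.** The Data collection part of Methods says that "Ten different locations will be used to report where the sentinel nodes were found" and numbers them. Items 1 to 4 lie along the aorta and vena cava. Items 5 to 10 are pelvic, starting with "iliaca communis left" and covering the common iliac, external iliac and obturator sites on each side. The list ends at the right obturator site, with no residual category. The same section requires that "the surgeon has to draw the location of the lymph nodes in an anatomical drawing", with reference to Figure 1.

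The Staging section of the Introduction summarises the national guideline on which regions matter most for nodal sampling. For the pelvis it names "the common, internal and external iliac vessels and the obturator fossa".

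The Study Design section describes the project as "mapping the lymphatic drainage of the ovaries". Sentinel node location is a secondary objective, and the Descriptive statistics section says that "the median and mean number of sentinel nodes and its main locations can be determined".

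**The concern.** The list that defines how locations are reported is narrower than the set of regions the protocol itself calls most important. The missing region is pelvic, and the pelvis is where the protocol admits least knowledge: under Main study parameter it says "The exact mechanism of drainage to pelvic area is still unclear". One of the two injection sites is the ovarian ligament on the median side, so drainage towards the pelvis is part of what is being observed. A mapping study should be able to record a result that its authors did not expect. A fixed list without a residual category cannot.

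At stake is the location result. Followed literally, the list would credit an internal iliac sentinel node to another site or drop it from the coded data. A reader could then not tell whether the internal iliac region receives no ovarian drainage or simply had no code.

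**Working it through.** **Step 1. Reproduce the stated count.** Para-aortic and caval 4 + common iliac 2 + external iliac 2 + obturator 2 = 10. This agrees with the protocol's figure.

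**Step 2. Set the Staging regions beside the Data collection codes.**

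| Region named under Staging | Matching code under Data collection |
|---|---|
| Para-aortic | yes |
| Paracaval | yes |
| Common iliac | yes, left and right |
| Internal iliac | none on either side |
| External iliac | yes, left and right |
| Obturator fossa | yes, left and right |

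Five of the six regions have a code. The internal iliac is the only one without.

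**Step 3. Express the gap for the pelvis, by side.** Staging implies 4 pelvic regions × 2 sides = 8. Data collection supplies 3 pelvic regions × 2 sides = 6. The shortfall is 8 − 6 = 2, and 2/8 = 25%. This counts categories; it is not an expected share of nodes or patients.

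**Step 4. Look for a residual category.** There is none. The gap is therefore wider than the internal iliac region. An inguinal node, a metastatic site that the Background section mentions from case reports, would have no code either.

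**Step 5. How likely is the gap to matter in this study?** The protocol gives no frequency of internal iliac sentinel nodes, so the per-patient frequency p below is an assumption. The number of evaluable patients, n = 20, comes from the Sample size calculation section. Treating patients as independent, the probability that at least one has such a node is 1 − (1 − p)^n:

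| Assumed p | 1 − (1 − p)^20 | Result |
|---|---|---|
| 0.02 | 1 − 0.98^20 = 1 − 0.668 | 33% |
| 0.05 | 1 − 0.95^20 = 1 − 0.358 | 64% |
| 0.10 | 1 − 0.90^20 = 1 − 0.122 | 88% |

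Even a fairly uncommon site could well occur once in a study of this size. The table does not show that it will.

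**Step 6. Trace what depends on the codes.** The main parameter is whether a sentinel node was found. The false-negative count compares the histology of sentinel and other nodes. The stopping rule uses the detection rate and the pace of inclusion. None of these uses the location code. Only the description of where sentinel nodes lie does.

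**The case against.** The strongest reply is that no information need be lost. The surgeon must draw each node on an anatomical figure, and with 20 evaluable patients an internal iliac node could be read off the drawing and described in the report. The protocol does not say in so many words that other sites are disallowed, and the Descriptive statistics section asks for locations per patient without referring to the ten codes. The Staging passage also serves another purpose: it relays guideline advice on sampling and does not define a sentinel node map. Finally, the assumed frequencies have no basis in the protocol, and the Background section says that lymphatic metastases are mainly para-aortic, a region with good coverage.

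Much of this is fair and limits the size of the point. The drawing may well preserve the raw position, although Figure 1 could not be seen in the text available here, so its labels and boundaries are unknown. The mismatch lies between the Introduction and the Methods, and does not prove that nodes will be misclassified. The frequencies only illustrate a range.

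What does not fall away is the reporting rule. The natural reading of the Data collection sentence is ten categories, and a drawing does not add an eleventh. No rule folds internal iliac nodes into the obturator or any other code, so two surgeons could code the same node differently. The Background section, besides stressing the para-aortic route, also calls pelvic metastases frequent. Nor is this a detail left to an analysis plan, since the protocol itself fixes the list at the point of data collection.

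**Conclusion.** The point holds. The reporting list leaves out one of the six regions that the protocol itself ranks as most important, on both sides, which is 2 of 8 side-specific pelvic categories. It also has no category for anything unforeseen. As written, coded results cannot show internal iliac drainage.

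The consequence is confined to one descriptive secondary result. The direction and size of any distortion cannot be derived from the protocol. The 33% to 88% range rests entirely on assumed per-patient frequencies of 2% to 10% and on all 20 evaluable patients contributing. The conclusion also assumes that Figure 1 does not itself introduce further reporting categories. This is worth correcting because location is a stated objective and the correction is easy; it does not threaten the feasibility conclusion.

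**What to change.** In the Data collection section and on the data form, add internal iliac left and internal iliac right, giving 10 + 2 = 12 named locations, and one residual category with a free-text field, giving 13 options. Check that the regions marked on Figure 1 agree with the extended list.

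As an option on which the point does not depend, use the same codes for sampled non-sentinel nodes and for residual nodes on the scintigram, so that the three sets of locations can be compared directly.

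The cost is an edit to one list and one form. No procedure, staff time or patients are added. If some patients have already been recorded, their drawings can be checked for nodes that belong in the new categories.
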